7 NIH REPORTING REQUIREMENTS/DATA AND SAFETY MONITORING PLAN

7.1 DEFINITIONS

Please refer to definitions provided in Policy 801: Reporting Research Events found [here](#).

7.2 OHSRP OFFICE OF COMPLIANCE AND TRAINING / IRB REPORTING

7.2.1 *Expedited Reporting*

Please refer to the reporting requirements in Policy 801: Reporting Research Events and Policy 802 Non-Compliance Human Subjects Research found [here](#). Note: Only IND Safety Reports that meet the definition of an unanticipated problem will need to be reported per these policies.

7.2.2 *IRB Requirements for PI Reporting at Continuing Review*

Please refer to the reporting requirements in Policy 801: Reporting Research Events found [here](#).

7.3 NCI CLINICAL DIRECTOR REPORTING

Problems expeditiously reported to the OHSRP in iRIS will also be reported to the NCI Clinical Director. A separate submission is not necessary as reports in iRIS will be available to the Clinical Director.

In addition to those reports, all deaths that occur within 30 days after receiving a research intervention should be reported via email to the Clinical Director unless they are due to progressive disease.

To report these deaths, please send an email describing the circumstances of the death to [name] at [contact] within one business day of learning of the death.

7.4 NIH REQUIRED DATA AND SAFETY MONITORING PLAN

7.4.1 *Principal Investigator/Research Team*

The clinical research team will meet on a regular basis (weekly) when participants are being actively treated on the trial to discuss each participant. Decisions about dose level enrollment and dose escalation if applicable will be made based on the toxicity data from prior participants.

All data will be collected in a timely manner and reviewed by the principal investigator or a lead associate investigator. Events meeting requirements for expedited reporting as described in Section [7.2.1](#) will be submitted within the appropriate timelines.

The principal investigator will review adverse event and response data on each participant to ensure safety and data accuracy. The principal investigator will personally conduct or supervise the investigation and provide appropriate delegation of responsibilities to other members of the research staff.

8 SPONSOR PROTOCOL/SAFETY REPORTING

8.1 DEFINITIONS

8.1.1 *Adverse Event*

Any untoward medical occurrence in a patient or clinical investigation subject administered a pharmaceutical product and which does not necessarily have a causal relationship with this treatment. An adverse event (AE) can therefore be any unfavorable and unintended sign (including an abnormal laboratory finding), symptom, or disease temporally associated with the use of a medicinal (investigational) product, whether or not related to the medicinal (investigational) product (ICH E6 (R2)).

8.1.2 *Serious Adverse Event (SAE)*

An adverse event or suspected adverse reaction is considered serious if in the view of the investigator or the sponsor, it results in any of the following:

- Death,
- A life-threatening adverse event (see Section [8.1.3](#))
- Inpatient hospitalization or prolongation of existing hospitalization
 - A hospitalization/admission that is pre-planned (i.e., elective or scheduled surgery arranged prior to the start of the study), a planned hospitalization for pre-existing condition, or a procedure required by the protocol, without a serious deterioration in health, is not considered a serious adverse event.
 - A hospitalization/admission that is solely driven by non-medical reasons (e.g., hospitalization for patient or subject convenience) is not considered a serious adverse event.
 - Emergency room visits or stays in observation units that do not result in admission to the hospital would not be considered a serious adverse event. The reason for seeking medical care should be evaluated for meeting one of the other serious criteria.

- Persistent or significant incapacity or substantial disruption of the ability to conduct normal life functions
- A congenital anomaly/birth defect

Important medical events that may not result in death, be life-threatening, or require hospitalization may be considered a serious adverse drug experience when, based upon appropriate medical judgment, they may jeopardize the patient or subject and may require medical or surgical intervention to prevent one of the outcomes listed in this definition.

8.1.3 *Life-threatening*

An adverse event or suspected adverse reaction is considered "life-threatening" if, in the view of either the investigator or sponsor, its occurrence places the patient or subject at immediate risk of death. It does not include an adverse event or suspected adverse reaction that, had it occurred in a more severe form, might have caused death. (21CFR312.32).

8.1.4 *Severity*

The severity of each Adverse Event will be assessed utilizing the CTCAE version 4.

8.1.5 *Relationship to Study Product*

All AEs will have their relationship to study product assessed using the terms: related or not related.

- Related – There is a reasonable possibility that the study product caused the adverse event. Reasonable possibility means that there is evidence to suggest a causal relationship between the study product and the adverse event.
- Not Related – There is not a reasonable possibility that the administration of the study product caused the event.

8.2 ASSESSMENT OF SAFETY EVENTS

AE information collected will include event description, date of onset, assessment of severity and relationship to study product and alternate etiology (if not related to study product), date of resolution of the event, seriousness and outcome. The assessment of severity and relationship to the study product will be done only by those with the training and authority to make a diagnosis and listed on the Form FDA 1572 as the site principal investigator or sub-investigator. AEs occurring during the collection and reporting period will be documented appropriately regardless of relationship. AEs will be followed through resolution.

SAEs will be:

- Assessed for severity and relationship to study product and alternate etiology (if not related to study product) by a licensed study physician listed on the Form FDA 1572 as the site principal investigator or sub-investigator.
- Recorded on the appropriate SAE report form, the medical record and captured in the clinical database.
- Followed through resolution by a licensed study physician listed on the Form FDA 1572 as the site principal investigator or sub-investigator.

For timeframe of recording adverse events, please refer to Section [6.1 Error! Reference source not found.](#). All serious adverse events recorded from the time of first investigational product administration must be reported to the sponsor.

8.3 REPORTING OF SERIOUS ADVERSE EVENTS

Any AE that meets protocol-defined serious criteria or meets the definition of Adverse Event of Special Interest that require expedited reporting must be submitted immediately (within 24 hours of awareness) to OSRO Safety using the CCR SAE report form.

All SAE reporting must include the elements described in section [8.2](#).

SAE reports will be submitted to the Center for Cancer Research (CCR) at: [contact] and to the CCR PI and study coordinator. CCR SAE report form and instructions can be found at: <https://ccrod.cancer.gov/confluence/display/CCRCRO/Forms+and+Instructions>.

8.4 SAFETY REPORTING CRITERIA TO THE PHARMACEUTICAL COLLABORATORS

All events listed below must be reported in the defined timelines to [contact].

CCR OSRO will send all reports to the manufacturer as described below.

- Serious adverse events (SAE) are defined above. If any SAE is required to be reported to the sponsor according to Section [8.1.2](#) (i.e. within 28 days of receiving drug or assessed as being possibly related to drug administration), the sponsor should inform Celgene of the SAE within 1 business day of being aware of the event. This must be documented on a Celgene SAE form or FDA 3500A or MEDWATCH form. This form must be completed and supplied to Celgene within 24 hours/1 business day. The initial report must be as complete as possible, including an assessment of the causal relationship between the event and the investigational product(s), if available. Information not available at the time of the initial report (e.g., an end date for the adverse event or laboratory values received after the report) must be documented on a follow-up MEDWATCH. A final report to document resolution of the SAE is required. The Celgene tracking number (PO-KS-NCI-0050) and the institutional protocol number should be included on SAE reports (or on the fax cover letter) sent to Celgene. A copy of the fax transmission confirmation of the SAE report to Celgene should be attached to the SAE and retained with the patient records.

All adverse experience reports must include the patient number, age, sex, weight, severity of reaction (mild, moderate, severe), relationship to study drug (probably related, unknown relationship, definitely not related), date and time of administration of test medications and all concomitant medications, and medical treatment provided. The investigator is responsible for evaluating all adverse events to determine whether criteria for “serious” and as defined above are present. The Investigator must keep copies of all AE information, including correspondence with Celgene and the IRB/EC on file for records retention information). The investigator is responsible for reporting adverse events to Celgene as described below.

In addition, if secondary malignancies that do not fall under the criteria for expedited reporting in section [7.2.1](#) are reported to the sponsor, the sponsor should inform Celgene of the malignancy within 7 working days of receiving the report using the same forms.

8.4.1 IND Annual Reports to Celgene

As the FDA has granted an IND number, it is a requirement of 21 CFR 312.33, that an annual report is provided to the FDA within 60-days of the IND anniversary date. 21 CRF 312.33 provides the data elements that are to be submitted in the report. The Annual Report should be filed in the study's Regulatory Binder, and a copy provided to Celgene Corporation as a supporter of this study as follows.

Celgene Corporation
Attn: Medical Operations
[name]
[name]
[contact]

8.5 REPORTING PREGNANCIES

Pregnancies and suspected pregnancies (including a positive pregnancy test regardless of age or disease state) of a female subject occurring while the subject is on investigational product (IP), or within 28 days of the subject's last dose of IP, are considered immediately reportable events. IP is to be discontinued immediately. The pregnancy, suspected pregnancy, or positive pregnancy test must be reported to the Sponsor within 24 hours, and the Sponsor will report this to Celgene Drug Safety within one business day by facsimile, or other appropriate method, using the Pregnancy Initial Report Form, or approved equivalent form. The Investigator will follow the female subject until completion of the pregnancy and up to 1 year to monitor the baby, and must notify CCR and the CCR in turn will notify Celgene Drug Safety immediately about the outcome of the pregnancy (either normal or abnormal outcome) using the Pregnancy Follow-up Report Form, or approved equivalent form.

Celgene Drug Safety Contact Information:

Celgene Corporation
Global Drug Safety and Risk Management
[name]
[name]
[name]
[contact]
e-mail: [contact]

All required pregnancy reports/follow-up to OSRO will be submitted to:

[contact] and to the CCR PI and study coordinator. Forms and instructions can be found here:

<https://ccrod.cancer.gov/confluence/display/CCRCRO/Forms+and+Instructions>.

8.5.1 Maternal exposure

If a participant becomes pregnant during the course of the study, the study treatment should be discontinued immediately, and the pregnancy reported to the Sponsor no later than 24 hours of when the Investigator becomes aware of it. The Investigator should notify the Sponsor no later than 24 hours of when the outcome of the Pregnancy becomes known.

Pregnancy itself is not regarded as an SAE. However, congenital abnormalities or birth defects and spontaneous miscarriages that meet serious criteria (Section [8.1.2](#)) should be reported as SAEs.

The outcome of all pregnancies (spontaneous miscarriage, elective termination, ectopic pregnancy, normal birth, or congenital abnormality) should be followed up and documented.

8.5.2 Paternal exposure

Male participants should refrain from fathering a child or donating sperm during the study and for 28 days after the last dose of Pomalidomide.

Pregnancy of the participant's partner is not considered to be an AE. However, the outcome of all pregnancies (spontaneous miscarriage, elective termination, ectopic pregnancy, normal birth, or congenital abnormality) occurring from the date of the first dose until 28 days after the last dose should, if possible, be followed up and documented.

8.6 REGULATORY REPORTING FOR STUDIES CONDUCTED UNDER CCR-SPONSORED IND

Following notification from the investigator, CCR, the IND sponsor, will report any suspected adverse reaction that is both serious and unexpected. CCR will report an AE as a suspected adverse reaction only if there is evidence to suggest a causal relationship between the study product and the adverse event. CCR will notify FDA and all participating investigators (i.e., all investigators to whom the sponsor is providing drug under its INDs or under any investigator's IND) in an IND safety report of potential serious risks from clinical trials or any other source, as soon as possible, in accordance to 21 CFR Part 312.32.

9 CLINICAL MONITORING

As a sponsor for clinical trials, FDA regulations require the CCR to maintain a monitoring program. The CCR's program allows for confirmation of: study data, specifically data that could affect the interpretation of primary study endpoints; adherence to the protocol, regulations, and SOPs; and human subjects protection. This is done through independent verification of study data with source documentation focusing on:

- Informed consent process
- Eligibility confirmation
- Drug administration and accountability
- Adverse events monitoring
- Response assessment.

This trial will be monitored by personnel employed by an CCR contractor. Monitors are qualified by training and experience to monitor the progress of clinical trials. Personnel monitoring this study will not be affiliated in any way with the trial conduct.

10 STATISTICAL CONSIDERATIONS

10.1 DEMOGRAPHIC DIVERSITY

- Subjects from both genders and all racial/ethnic groups are eligible for this study if they meet the eligibility criteria. Outreach efforts will be made to extend accrual to a representative population.
- It should be noted that in the US, KSHV seroprevalence is relatively low in females with or without HIV infection. However, recent HAMB studies have increasingly accrued female immigrants from Africa and transgendered persons.

10.2 AGE EXCLUSION

Patients under the age of 18 will be excluded. KSHV infection and its complications including KS and HIV infection are each very rare in North American children, making it unlikely that pediatric cases of KS will be seen.

10.3 ACCRUAL TIMELINE

As the subjects being evaluated for toxicity may or may not be evaluable for response as part of the stringent eligibility response cohort, after an amendment to evaluate HIV positive and HIV negative patients in separate cohorts, the study may require enrolling from 25 to 40 subjects, depending on the final dose level and the number of those evaluated for toxicity that may also be evaluable for response.

It is anticipated that ten to twelve patients per year may enroll onto this trial. In order to allow for the possibility of a very small number of inevaluable subjects, the accrual ceiling will be set at 40 subjects. Accrual is expected to be completed within two to three years.

HAMB has an established cohort of KSHV-seropositive subjects, most with KS or a history of KS through protocol 01-C-0193 and other ongoing studies of KS, KSHV-MCD and KSHV-associated lymphoma as well as a referral base in the HIV and infectious disease community which together provide a population to support projected accrual. Accrual will be regularly reviewed against projections, and consideration given to additional promotional activities should it fall short of projections.

10.4 STATISTICAL ANALYSES

An initial toxicity assessment phase of the trial will be conducted in which up to six subjects will be treated with pomalidomide at 5mg daily for 21 days of a 28 day cycle. If two or more subjects experience a DLT within the first two cycles (eight weeks), then up to six subsequent subjects will be treated at 3 mg daily for 21 days of a 28 day cycle. The highest dose at which zero or one of six subjects experience a DLT during the first two cycles (eight weeks) will be used to determine potential clinical activity.

Once the dose for assessment of clinical activity is determined, two expansion cohorts will be established to investigate response rate. These will be established with the goal of enrolling ten evaluable HIV negative patients, and fifteen evaluable HIV positive patients. Where KS is HIV-associated, these latter subjects will have somewhat more stringent entry criteria with respect to KS not responding to HAART to enable a better assessment of any anti-tumor activity uncomplicated by tumor responses associated with HAART initiation (inclusion criterion **2.1.1.15** above). Subjects treated at the dose chosen for assessment during the toxicity

assessment phase who met these additional eligibility criteria at study entry will be considered evaluable for response for this part of the study, in the appropriate cohort.

There are two circumstances under which an individual subject's dose could be de-escalated: first if two other subjects on the same dose level experience a DLT (Section 3.1.3), and second if the subject experiences a non-thromboembolic DLT on the higher dose level which resolves within 28 days (Section 3.3). In either instance, if the subject is evaluable they will be considered part of the initial (higher) dose cohort for the purposes of evaluating response.

At the dose for assessment of clinical activity, two cohorts of patients will be evaluated according to their HIV status as follows:

Of the ten evaluable subjects enrolled in the HIV negative expansion cohort, the probability of three or more responding (complete responders plus partial responders) is 83.3% if the true probability of a response is 40%, and 7.0% if the true probability of a response is 10%. Thus, obtaining at least three subjects with a response in the ten HIV negative evaluable subjects is more likely to be consistent with a $\geq 40\%$ true response rate than with a $\leq 10\%$ true response rate. This outcome (three or more responders) will be considered sufficiently positive for further investigation of the agent in this group.

Of the fifteen evaluable subjects enrolled in the HIV positive expansion cohort, the probability of four or more responding (complete responders plus partial responders) is 90.9% if the true probability of a response is 40%, and 5.6% if the true probability of a response is 10%. Thus, obtaining at least four subjects with a response in the 15 evaluable HIV positive subjects is more likely to be consistent with a $\geq 40\%$ true response rate than with a $\leq 10\%$ true response rate. This outcome (four or more responders) will be considered sufficiently positive for further investigation of the agent in this group. As of the submission of amendment G, fifteen evaluable subjects in the HIV positive expansion cohort have been accrued to address the primary question of assessing the anti-tumor effect of pomalidomide in those patients. The responses for these 15 subjects will be reported together with the 7 subjects enrolled to date in the HIV negative expansion cohort. The protocol allows for accrual up to 18 HIV (+) patients and 10 HIV (-) patients. As the endpoint for activity has been reached for the HIV (+) patients at this time, the initial analysis describing the activity of pomalidomide in KS will include only patients entered up until this time. Any additional subjects accrued after this point in either cohort (up to 3 in each cohort) will be primarily evaluated for correlative endpoints; they will also be included in any description of long term clinical outcomes at a later point.

At the conclusion of the trial, the response rates from the two cohorts will be compared and if they are sufficiently similar ($p > 0.30$ by a two-tailed Fisher's exact test), in addition to being reported separately, they can be pooled together and also reported in that manner. Also, after the all patients have been evaluated for response, 95% confidence intervals will be formed about the response rate in both cohorts, as well as together, if sufficiently similar. The maximum confidence interval widths would be $\pm 32\%$ with 10 patients, $\pm 26\%$ with 15 patients, and $\pm 20\%$ with 25 patients.

To allow for the possibility of different accrual rates between these two cohorts in this rare disease, up to an additional three subjects may be accrued to the evaluable HIV positive cohort (for a maximum of eighteen) in the case that ten evaluable HIV negative subjects have not yet been accrued at the time that accrual of evaluable HIV positive subjects reaches fifteen. In the

event that 16 to 18 HIV positive patients are enrolled, 4 or more responders will still be needed to be considered sufficiently positive for further investigation.

Response rates will be estimated for pomalidomide. Survival analysis will be performed using Kaplan-Meier methods. Progression-free survival will be defined as the time from Day 1 of a given intervention until progression *requiring a change in therapy*. Event-free survival will be defined as the time from Day 1 of a given intervention until progression *requiring a change in therapy* or death as a result of any cause. All results will be carefully reported in the context of the limited size of the study.

For those subjects who obtain a clinical complete or partial response or clinical benefit from initial treatment with pomalidomide, and subsequently again manifest KS requiring therapy while not receiving pomalidomide, an additional course of treatment with pomalidomide may be offered as described in Section 3.1.6. Based on responses seen at the time of this amendment (January 2013) and our experience with treatment of KS, it is anticipated that approximately 3-6 subjects will potentially be eligible for and receive an additional course of therapy, but this estimate will be refined as further subjects are enrolled and become assessable for response. The scientific objective of this cohort will be to explore the safety and tolerability of a second course of pomalidomide in patients who had previously benefited from the agent: this exploration will comprise a secondary objective for the protocol overall. As a further objective, tumor response rates in this cohort will also be evaluated with exploratory intent; and virologic and immunologic correlative studies will be performed for comparison with those obtained during the first treatment course. For those subjects treated with this additional course, a new tumor baseline will be taken, and the subsequent response to treatment from this baseline will be determined. The fraction of the patients who receive the extra course who respond to treatment (complete responders plus partial responders) will be determined and estimated along with a 95% confidence interval. The results obtained following this subsequent treatment will be presented separately from those for the initial treatment.

Each of the correlative analyses will be evaluated with exploratory intent, using non-parametric methods generally, and without formal adjustment for multiple tests performed. Results will be presented in the context of a hypothesis generating study.

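### Does keeping the four-responder rule for 16 to 18 HIV-positive patients undermine the error rates that Section 10.4 gives for 15?

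*Combined protocol and SAP*

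**What the plan says.** All the relevant text is in Section 10.4 of the combined protocol and SAP.

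- **The rule.** "Of the fifteen evaluable subjects enrolled in the HIV positive expansion cohort, the probability of four or more responding" is put at 90.9% for a 40% true rate and 5.6% for a 10% true rate. Four or more responders would justify further study in this group, because that result fits a rate of 40% or more better than one of 10% or less. The HIV-negative rule (3 of 10) has its own figures, 7.0% and 83.3%.
- **Status at amendment G.** The section reports that "fifteen evaluable subjects in the HIV positive expansion cohort have been accrued to address the primary question of assessing the anti-tumor effect". It then gives a reason: "As the endpoint for activity has been reached for the HIV (+) patients at this time". The consequence it draws for the first report is that "the initial analysis describing the activity of pomalidomide in KS will include only patients entered up until this time". Later patients have another main purpose: "Any additional subjects accrued after this point in either cohort (up to 3 in each cohort) will be primarily evaluated for correlative endpoints". They also enter later descriptions of long-term outcome.
- **The extension.** Up to three more evaluable HIV-positive patients may join if the HIV-negative cohort has not reached ten by the time the HIV-positive cohort reaches fifteen. The cut-off then stays at 4: in the "event that 16 to 18 HIV positive patients are enrolled, 4 or more responders will still be needed to be considered sufficiently positive".
- **End of trial.** The cohorts are compared, and 95% confidence intervals formed, once all patients have been evaluated for response.

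**The concern.** Two things look wrong at first.

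First, a fixed count of responders is easier to reach with more patients. Holding the cut-off at 4 while the cohort grows from 15 to 18 raises the chance of passing an inactive drug, yet the only figures shown are for 15. A reader who applied 5.6% to a decision made on 18 would understate that chance.

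Second, the amendment G text centres the activity analysis on the first 15, whereas the extension sentence still states a rule for 16 to 18. Reaching the endpoint could mean that 15 patients had been accrued or that 4 had responded; the text does not say which. If only accrual is meant, a cohort with 3 responders among the first 15 and 1 among the next 3 fails on one denominator and passes on the other. At stake are which denominator the HIV-positive decision uses and which error rates belong to it.

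**Working it through.** **Inputs (Section 10.4).** Cut-off 4; n = 15, or 16 to 18 if extended; true response rates p = 0.10 and 0.40.

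**Formula.** P(X ≥ 4) = 1 − Σ C(n,k) pᵏ (1 − p)ⁿ⁻ᵏ, summed over k = 0 to 3.

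**Step 1: reproduce the plan's figures at n = 15.**

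- p = 0.10: 1 − (0.2059 + 0.3432 + 0.2669 + 0.1285) = 0.0556 from unrounded terms. Printed: 5.6%.
- p = 0.40: 1 − (0.0005 + 0.0047 + 0.0219 + 0.0634) = 0.9095. Printed: 90.9%.

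The HIV-negative rule (3 or more of 10) gives 0.0702 and 0.8327, matching 7.0% and 83.3%.

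**Step 2: same cut-off, all enrolled patients counted.**

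| n | P(≥ 4), p = 0.10 | P(≥ 4), p = 0.40 | Ratio |
|---|---|---|---|
| 15 | 5.6% | 90.9% | 16.4 |
| 16 | 6.8% | 93.5% | 13.7 |
| 17 | 8.3% | 95.4% | 11.5 |
| 18 | 9.8% | 96.7% | 9.8 |

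The ratio (0.40 column over 0.10 column) measures the plan's argument that passing fits 40% better than 10%. At 18 patients passing is still 9.8 times as probable under 40%.

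**Step 3: would another cut-off restore 5.6%?** A cut-off of 5 gives 1.7% / 83.3% at n = 16, 2.2% / 87.4% at n = 17 and 2.8% / 90.6% at n = 18. No whole number reproduces 5.6%: 4 lies above it and 5 well below.

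**Step 4: how often would 15 and 18 disagree?** Responders only accumulate, so 4 or more of 15 is also 4 or more of 18. Disagreement needs 3 or fewer among the first 15 and then 4 or more in total. Its probability is therefore the difference P(≥ 4 of 18) − P(≥ 4 of 15):

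- p = 0.10: 0.0982 − 0.0556 = 0.0426, or 4.3%.
- p = 0.20: 0.4990 − 0.3518 = 0.1471 (unrounded inputs), or 14.7%.
- p = 0.25: 0.6943 − 0.5387 = 0.1556, or 15.6%.
- p = 0.30: 0.8354 − 0.7031 = 0.1323, or 13.2%.
- p = 0.40: 0.9672 − 0.9095 = 0.0577, or 5.8%.

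Most of this comes from exactly 3 responders in 15. Given that result, three more patients bring the total to 4 or more with probability 1 − 0.9³ = 27.1% at p = 0.10 and 1 − 0.6³ = 78.4% at p = 0.40. Exactly 3 of 15 has probability 0.1285 and 0.0634, so the whole path has probability 0.1285 × 0.271 = 3.5% and 0.0634 × 0.784 = 5.0%.

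**Step 5: the two parts of the section side by side.** The amendment G text describes an initial analysis, limited to patients entered by then. The paragraphs on comparison and confidence intervals concern the end of the trial, when everyone has been assessed. A first report on 15 followed by a final account of up to 18 is a coherent sequence. The extension sentence fixes the number of responders required; it does not say that responses in patients 16 to 18 count towards it.

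**The case for a change.** The strongest case for a change is that the section prints probabilities for both planned cohort sizes but none for the extended sizes, although it states a rule for them. At 18 patients the chance of passing at a 10% true rate is 0.0982 / 0.0556 = 1.8 times the printed value, and above the 7.0% accepted for the HIV-negative cohort. The amendment G text limits only the initial analysis and does not withdraw the extension rule. A sentence or two would name the denominator at no cost in patients or data.

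The arithmetic stands, and so does the observation that no denominator is named. The case weakens on what follows from that:

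- The 9.8% needs all three extra patients enrolled and all counted. The plan does not say the latter, and it assigns those patients mainly to correlative work. If the decision rests on 15, the printed 5.6% is the right figure.
- The extension depends on slow HIV-negative accrual, not on observed responses, and the cut-off for it is written down. It is not a licence to keep enrolling until the rule is met.
- Fixing the decision at the first 15 is not free. Compared with 18 it lowers the chance of passing by 5.8 points at a 40% true rate, but by 13 to 16 points at 20% to 30%. Section 10.4 says the 15 were already accrued by amendment G, so the choice would now come late and possibly with responses known. It would change nothing if 4 of the 15 had responded.

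**Conclusion.** No change is needed. Every printed figure is correct. The plan declares no alpha, antitumor effect is a secondary objective to be explored in a preliminary way (Section 1.1.2), and the rule decides only whether further study is worthwhile. The reasoning behind the cut-off survives at 18 patients, where passing is 9.8 times as probable at 40% as at 10%. The initial and end-of-trial analyses can be read as successive reports.

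What remains is a gap in detail: the figures for 16 to 18 and the decision denominator. Any analyst can compute the first from the stated rule, and a report that gives responders over patients for the first 15 and for the full cohort shows whether the second matters. It cannot matter if 4 or more of the first 15 responded. Otherwise the probability that counting 18 rather than 15 alters the decision is 4.3% at a 10% true rate, 5.8% at 40% and at most about 16% in between; these are probabilities before any response is seen. They assume independent responses with a common rate and three extra patients who are all evaluable and all counted.
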